#### 10.6 Expected Duration of Trial.

Specify the expected clinical participation and define the end of the trial. This can be the full study duration e.g. first patient first visit to last patient last visit including follow up.

The first participant is expected to start the trial around 1st November 2017 and the last participant will be tested by 1st January 2021.

# **11. Trial Procedures**

The following procedure will be followed in this study:

1. The participant will express interest in the study either in response to an advertisement (attached to this proposal), or through information provided by their clinicians at CAMHs or through Trust Consent for Contact (C4C) mechanisms.

2. The participant and the parents will then be sent a copy of the information sheet describing the research study and additional information on the methodologies used. They will receive comprehensive information about the study and the type of screening questions that they will be required to answer on a consent form on the day of the study at least 24 hours before the appointment.

3. If the participant or the parent contacts one of the researchers (by telephone, email, or in person) to receive further information, s/he will be given the opportunity to ask any questions about the study, and to take more time to think about it if they so wish. If they express interest in participating in the study, we will take their contact details to arrange a convenient appointment time.

4. In the week prior to the first testing session, participants will come to the Institute of Psychiatry, Psychology and Neuroscience to complete the IQ testing and to fill in any questionnaires that relates to the main experiment (clinical questionnaires will be filled out by the parents). This visit will also provide the volunteer and his/her parent with an opportunity to ask questions about the study and to familiarise themselves with the study protocol and the facilities. The children will also have to perform a computer test battery that measures attention, inhibition and timing skills.

All participants will be randomly allocated to an experimental (fMRI-NF) and a control group (sham fMRI-NF). The two groups will be matched for age and medication status.

5. At the beginning of any experimental session, the researcher will explain the procedure in detail. Participants will be scanned 4 times in a new GE MR750 3T scanner (General Electrics Milwaukee, USA) for 60min.

Patients will be randomly allocated to active (N = 50) or control groups (N = 50) stratified by age and medication status.

The active group will be trained to upregulate right inferior frontal lobe activation throughout 14 RT-fMRI-NF runs (7.5 min each, 2-5 sessions per scan), totalling 4 fMRI sessions of 60 minutes over two weeks. In order to prove specificity of NF effects, the control group will have the exact same procedure, but will obtain non-contingent NF from the NF data of one of the active participants.

6. NF sessions (60 min) will consist of 4 runs of each of six activation (upregulation) blocks (40s each), separated by 7 baseline blocks (relaxation/no upregulation), starting and ending with a baseline block (ABABABABABA). The fMRI interface system (provided by [name], Laureate Institute for Brain Research, USA) transfers the images from the MRI

scanner to an external workstation as soon they are reconstructed. Images are then preprocessed using AFNI (afni.nimh.nih.gov/afni), which has built-in real-time capacities. An image mask composed of preselected regions of interest (ROIs) is then applied to the preprocessed images in order to extract the mean neural activity in each selected region. As a new brain volume is acquired every repetition time (2s in this study), AFNI calculates a new set of values for each ROI. The values for each ROI are then sent to a second PC, where they are combined to generate a running time-series for the feedback signal. Finally, this feedback signal is displayed within the scanner in a child-friendly manner. We will present as feedback to the participants their brain activation of rIFG (sham-feedback in controls), using a graphical representation of a rocketeer moving towards the sky, passing through clouds, and ultimately reaching some planets every time they managed to increase the activation of the target region.

Participants cannot easily verbalise the most efficient strategies for successful NF and it is hence more efficient to let participants find their own strategy rather than prescribing one (Birbaumer et al., 2009). The activation will be evaluated in real-time, after each fMRI acquisition, by using the latest reconstructed dataset, i.e. the brain activation during the last 2 seconds.

7. After the last session, the children will be asked to do again the computerised tests of attention, inhibition and timing to test whether they have improved in these skills after the training. The parents also will have to fill in the clinical questionnaires and the side effects scale.

8. After 6 months (after the training) the parents will be asked to fill in (or answer by telephone) the ADHD severity questionnaire and the child will have to repeat the cognitive test battery one more time.

9. The participants will receive up to £180. We will give them tokens for each visit throughout the 2 week training. They will receive money in exchange for the tokens at the end of the training and at the follow-up assessment. We will also reimburse their travel costs.

# 11.1 Laboratory Tests

None

# **12. Assessment of Efficacy**

The ADHD Rating scale is the primary efficacy measure which is a standard measure used in ADHD to measure effects of pharmacological and non-pharmacological treatment. The ADHD index of the Conners Parent Rating Scale is a commonly used secondary efficacy measure for behavioural improvement in ADHD.

# 12.1 Primary Efficacy Parameters

ADHD symptoms as measured on the ADHD-Rating Scale (ADHD-RS). (Dupaul et al. 1999).

# 12.2 Secondary Efficacy Parameters

The ADHD Index of the Conners Parent Rating Scales (CPRS).

#### 12.3 Procedures for Assessing Efficacy Parameters

The efficacy measures are parent rated behaviour scales for ADHD behaviours which will be filled in by the parents before and after the treatment and at follow-up assessment.

# 13. Assessment of Safety

# 13.1 Specification, Timing and Recording of Safety Parameters.

MRI is considered safe and non-invasive and there are no side effects are usually recorded.

We will measure side effects before and after the treatment as well as adverse effects. However, we do not expect any side or adverse effects as the methodology is safe in children and we found no side or adverse effects in our pilot study.

However, there is a slight risk that the scanner is sometimes perceived as unpleasant and uncomfortable. The researchers will be sensitive to this possibility and will suspend testing sessions at the request of the participant or at the first signs of distress and discomfort. The participant will be informed that he/she is free to terminate the scanning session whenever he/she wants to. Alerting mechanisms ensure easy communication and radiographers will constantly check that the participant is content to remain in the scanner.

Adolescents are sometimes anxious about the scanner – they will be shown the "mock scanner" to familiarise them with the scanner beforehand and they will be able to tell in the first scan whether they are happy to be scanned 4 times. Every effort will be made to ensure that they do not feel anxious or claustrophobic. However, if they feel that the scanner is frightening to them, they will not have to participate. The same applies for adolescents who feel claustrophobic in the scanner.

The scanner is also noisy and this may be unpleasant for some children. We will therefore expose them to the noise beforehand in the mock scanner. If the children feel that they dislike the noise, they do not have to participate. Also, in order to minimize the discomfort of the noise, we will provide all participants with headphones that are specifically designed for MRI scanners to reduce the noise level. This is standard procedure for all scanning subjects at the IOP.

# 13.2 Procedures for Recording and Reporting Adverse Events

We will measure side effects before and after the treatment as well as adverse effects. However, we do not expect any side or adverse effects as the methodology is safe in children and we found no side or adverse effects in our pilot study.

13.2.1 Adverse events that do not require reporting

None are expected.

# 13.3 Stopping Rules

Changes in safety rules are very unlikely and there are no particular reasons why the trial should be stopped.

# 14. Statistics

Behavioral data and fMRI analysis will be conducted using statistical techniques with a primary focus on repeated measures ANOVAs (within-subject factor TIME; between subject factor GROUP). Supplementary analyses may include parametric correlation analyses (for example Pearson's correlation tests).

The named researchers have substantial and proven experience in these types of analyses, having published and taught extensively.

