# 2. Study Synopsis

TITLE OF CLINICAL TRIAL:	fMRI Neurofeedback as a novel neurotherapy for children with ADHD				
Protocol Short Title/ Acronym:	AFNIS				
Study Phase If Not Mentioned In Title:	Proof of concept randomised controlled trial				
Sponsor Name:	King's College London, South London and Maudsley Trust				
Chief Investigator:	[name]				
UKCRN Number:					
REC Number:	230303				
Medical Condition Or Disease Under Investigation:	Attention Deficit Hyperactivity Disorder (ADHD)				
Purpose Of Clinical Trial:	Powered proof of concept experimental randomized placebo-controlled double-blind trial to test the mechanism and clinical efficacy of real-time fMRI neurofeedback (fMRI-NF) of right inferior frontal cortex (rIFC) compared to sham fMRI-NF in ADHD children				
Primary Objective:	To examine whether fMRI neurofeedback of right frontal cortex (rIFC) in ADHD children will 1) reduce their ADHD symptoms				

	
 
increase activation in rIFC over the 14 sessions
 
			
Secondary Objective(s):	
 
To test whether the fMRI neurofeedback will : 
 
improve other clinical ADHD severity measures
 
improve performance on a battery of cognitive tasks relevant to ADHD
 
will increase activation in rIFC in a Stop fMRI task
 
Will increase the activation of an entire functional network connected with the rIFC
 
has no side effects
 
will improve clinical and cognitive measures longer-term, 6 months after training
 

			
Trial Design:	Randomised controlled double-blind trial			
Endpoints:	
 
Performance on a cognitive task battery of cognitive control tasks
 
Parent ratings on the ADHD Rating scale
 
			
Sample Size:	100 ADHD children, 10-18 years			
Summary Of Eligibility Criteria:	Meeting clinical diagnosis for Attention-Deficit Hyperactivity Disorder (ADHD); male; age range 10- 18 years; stable medication or non-medicated; no comorbid conditions other than oppositional defiant and conduct disorder; IQ > 80.			
Intervention (Description, frequency, details of delivery)	Participants will undergo four hourly fMRI scans with feedback of their activation of rIFC. They will be asked to modulate this activation via a video-game that is connected to the activity of the rIFC.			
Comparator Intervention:	Sham real-time fMRI neurofeedback			
Maximum Duration Of Treatment Of A Subject:	2 weeks			
Version And Date Of Final Protocol:	Version 2 27/10/2017			

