However, blinded randomised controlled studies of EEG-NF only show trend-level efficacy. Real-time functional magnetic resonance imaging neurofeedback (fMRI-NF) acts more rapidly, presumably due to its superior spatial resolution, allowing more specific targeting of brain regions. Furthermore, it can target deep cortical and subcortical regions such as the rIFC that are most consistently impaired in ADHD. fMRI-NF studies have been promising in other disorders in remediating key neurofunctional substrates and improving

The electronic version of this document is the latest version. It is responsibility of the individual to ensure that any paper material is the current version. Printed material is uncontrolled documentation.

associated behaviours. Our pilot feasibility RT-fMRI-NF study showed that ADHD children can learn to self-regulate rIFC within 11 fMRI-NF sessions of 8.5 minutes each, with significant transfer effects (i.e., after the training they are asked to self-regulate their brain without the NF to show they have learned it) and that this is associated with improved clinical symptoms, cognitive improvements and enhanced rIFC activation during a fMRI task of selfcontrol. However, potential placebo effects cannot be ruled out as we did not include a sham control condition. We therefore plan here a larger and more definite data-driven proof of concept study to test the efficacy of 15 sessions of 7.5 minutes of fMRI-NF of rIFC in 100 children with ADHD, randomised into active and sham control groups, on improving ADHD behaviour, brain function and cognition.

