#### 7.1.1 Primary endpoints

1) ADHD symptoms as measured on the ADHD-Rating Scale (ADHD-RS). (Dupaul et al. 1999).

2) Monotonic increase in inferior frontal lobe activation across the 14 neurofeedback sessions in the active group.

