# 8. Trial Intervention

# 8.1 Therapy/Intervention Details

Participants will be scanned 4 times in a new GE MR750 3T scanner (General Electrics Milwaukee, USA) for 60 min. Patients will be randomly allocated to active (N = 50) or control groups (N = 50), stratified by age and medication status. The active group will be trained to upregulate right inferior frontal lobe activation throughout 14 fMRI-NF sessions (7 min 30sec each, 2-5 sessions per scan), totalling 4 fMRI scan hours over two weeks. The first of the 4 visits will contain the 6min fMRI task and 2 NF sessions. Visit 2 and 3 will contain 5 NF sessions each followed by a transfer session without feedback. Visit 4 will contain 3 NF sessions, the Stop fMRI task, and a transfer session. The control group will have the exact same procedure, but will obtain non-contingent NF from the NF data of one of the active participants.

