# 14.1 Sample Size

100 ADHD adolescents will be enrolled in the study, randomised into the fMRI-NF of rIFC (N = 50) and the sham NF (N = 50).

The estimates of a clinically relevant effect size were calculated from our IOPPN pilot study on fMRI-NF in ADHD adolescents using the exact same outcome measures. ES for clinical efficacy in our pilot study was around 0.6. For a mean ES of 0.6 and a power of 80% with a p < 0.05, we would need 45 children in each group. We hence powered the study to include 50 children in each group accounting for a generously estimated potential drop-out rate of up to 10%. Our pilot study was well tolerated by ADHD children who liked the Neurofeedback "game" and we had a drop-out rate of only 5%, which is lower than the 6-10% drop-out rate we have had for studies of repeated fMRI scans under several medication conditions.

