#### 14.3 Analysis

A description of the statistical methods to be employed, including timing of any planned interim analyses should also be provided The level of significance that is to be used in each trial analysis must be stipulated, together with the procedure(s) for accounting for any missing, unused, and spurious data. Procedures for reporting any deviation from the original statistical plan should be described and justified. The data set for any analysis must be clearly stipulated (e.g. "all subjects", "randomised subjects", "intent to treat") and the population(s) should be clearly defined. Define the trial stopping rules if appropriate.

For all analyses, repeated measures ANOVAs will be conducted with TIME as within-subject factor and GROUP as between subject factor. Supplementary analyses may include parametric correlation analyses (for example Pearson's correlation tests).

The named researchers have substantial and proven experience in these types of analyses, having published and taught extensively.

For missing data, imputations will be used. The individual estimates from the multiply-imputed datasets will then be used to calculate a combined estimate by applying Rubin's Rules [Little and Rubin, 2002].

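### The second primary endpoint is an ordered rise in activation over runs, but the analysis fixed for it is an ANOVA with no trend contrast named, so a significant result would not show an increase

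*Protocol*

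**What the plan says.** Protocol section 7.1.1 lists two primary endpoints. The second is "Monotonic increase in inferior frontal lobe activation across the 14 neurofeedback sessions in the active group". The synopsis gives the matching objective in directional terms: to "increase activation in rIFC over the 14 sessions".

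The analysis is stated twice. Section 14 puts the "primary focus on repeated measures ANOVAs (within-subject factor TIME; between subject factor GROUP") and says that this covers both behavioural and fMRI data. Section 14.3 is broader: "For all analyses, repeated measures ANOVAs will be conducted with TIME as within-subject factor and GROUP as between subject factor". The only other technique named for testing is correlation, as a supplement. No linear or other trend contrast, ordered alternative or working definition of monotonic appears.

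Section 7.2 says that the trial tests superiority of active over sham feedback. Section 14.1 bases the sample size on clinical efficacy: "For a mean ES of 0.6 and a power of 80% with a p < 0.05, we would need 45 children in each group". It gives no effect size, slope or SD for activation.

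The number of runs is not consistent. Section 8.1 trains the active group "throughout 14 fMRI-NF sessions (7 min 30sec each, 2-5 sessions per scan"), and the synopsis and sections 7.1.1 and 11 also say 14. Section 6 refers to the "efficacy of 15 sessions of 7.5 minutes of fMRI-NF of rIFC". Section 11 also says "NF sessions (60 min) will consist of 4 runs of each of six activation (upregulation) blocks".

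**The concern.** The endpoint asks about direction and order. The F test for a within-subject factor with 14 levels asks only whether the run means differ in any way, or, for TIME x GROUP, whether the two profiles differ in any way. Shuffling the run labels leaves F unchanged. A significant result could come from an atypical first run, a zig-zag or a decline. A non-significant one could sit on top of a steady rise whose signal is spread over 13 degrees of freedom.

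The deciding term is also unclear. The endpoint is confined to the active group, while the fixed model has a GROUP factor. In that model the TIME main effect averages over both arms, and TIME x GROUP compares the shapes of the two arms. Neither is a test of a rise in the active arm, and they can disagree. This endpoint carries the trial's claim about mechanism, so a choice of term or shape made after seeing the data would weaken that claim.

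**Working it through.** **1. The plan's own figure.** For a standardised difference of 0.6, two-sided 5% and 80% power, the t-based calculation gives 44.6, so 45 per group; 45/0.9 = 50 with 10% drop-out. Power at 45 per group is 80.4%. The stated figure reproduces, but it concerns the clinical outcome. Everything below on activation therefore needs assumed effect sizes.

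**2. Direction.** The omnibus non-centrality depends on the sum of squared deviations of the run means. It is the same for a rise, its mirror image and any reordering. This holds whatever the effect size.

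**3. Power with a common slope.** Assumptions: 14 equally spaced runs, linear rise, sham flat, independent errors of equal variance, two-sided 5%.

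- GROUP x linear run, 45 per arm: 80% power on F(1, 88) needs non-centrality 8.02. The same 8.02 on F(13, 13 x 88 = 1144) gives **38.4%**.
- Active arm alone, 50 children: the same calibration on F(1, 49), carried to F(13, 13 x 49 = 637), gives **38.9%**.

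**4. The same in terms of the size of the rise.** Let d be the rise from first to last run in within-child residual SDs, n = 50 per arm, b = d/13, and the sum of squared centred run numbers 227.5. Non-centrality is n x b² x 227.5 in the active arm and half that for GROUP x TIME. For d = 0.5 this is 50 x 0.001479 x 227.5 = 16.8, and 8.4.

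| Assumed rise d | Active arm: omnibus | Active arm: linear | GROUP x TIME: omnibus | GROUP x linear |
|---|---|---|---|---|
| 0.3 | 28.3% | 67.5% | 14.8% | 40.7% |
| 0.5 | 76.1% | 98.0% | 40.5% | 81.9% |
| 0.6 | 92.0% | 99.8% | 58.4% | 93.1% |
| 1.0 | about 100% | about 100% | 98.6% | about 100% |

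**5. Power when children differ in slope.** Let s be the between-child SD of the rise, in residual SDs. The variance of a child's estimated rise is s² + 169/227.5 = s² + 0.743. With 45 per arm, the GROUP x linear contrast has 80% power at d = sqrt(8.02 x (2/45) x (s² + 0.743)): 0.51 for s = 0 and 1.30 for s = 2. Simulated power of the Greenhouse-Geisser-corrected TIME x GROUP test at those rises, to within a point or two:

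| Slope SD s | 0 | 0.5 | 1.0 | 1.5 | 2.0 |
|---|---|---|---|---|---|
| Omnibus, linear held at 80% | 34% | 48% | 64% | 73% | 77% |

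Slope variation inflates the error of the linear contrast fully but is averaged over 13 dimensions in the omnibus error term, so the gap closes. The first entry lies below 38.4% because of the sphericity correction.

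**6. Cost of the linear contrast.** If activation rises evenly to run 3 and then stays flat, the linear contrast captures 35% of the pattern's sum of squares; if it rises to run 5, 58%.

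**7. Number of runs.** Section 8.1's visit breakdown is 2 + 5 + 5 + 3 = 15, against its own stated total of 14. Four runs at each of four visits, if section 11's figure applies throughout, would be 16. The count sets both the degrees of freedom and the contrast weights.

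**The case against.** The strongest reply is that a linear contrast is part of repeated-measures ANOVA. The protocol neither names nor excludes one, and contrasts are often left to an analysis plan. A reader might infer that the stated method is incapable of testing an increase; the text does not support that. What stands is narrower. The protocol does fix a method for every analysis, and the tests which that method yields by default do not answer the endpoint it states.

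A reader might also infer that the omnibus test always forfeits at least half of the attainable power. The documents give no activation effect size to support this. With a common slope the ratio is 38/80 = 48%, with large slope variation it is 77/80 = 96%, and for a large rise both tests are near 100%.

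A third tempting reading is that monotonic means every run mean must exceed the one before. The protocol never states such a success rule, so it should not be judged on one. The word does need a definition.

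Two criticisms apply to the remedy as well. A two-sided linear contrast is also significant for a fall, so the sign must be part of the rule. A non-significant slope does not exclude a rise either. Finally, linear is narrower than monotonic, and for learning that plateaus early the loss in step 6 is material.

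**Conclusion.** The mismatch between endpoint and test is real and can be seen in the protocol's own text. It does not depend on any assumed number: a significant 13-df TIME or TIME x GROUP result would not show a rise in the active group. The power loss for a steady rise is conditional. It runs from about 38% against 80% with a common slope to about 77% against 80% when children's slopes vary widely, assuming 14 equally spaced runs, a linear rise, a flat sham arm and two-sided 5%. This should be fixed, but it does not invalidate the design, because a suitable contrast sits within the same family of models.

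**What to change.** - In section 7.1.1, define the monotonic increase operationally as a positive trend in activation over runs.
- In section 14.3, pre-specify one 1-df linear-run contrast as decisive, with a positive slope required, from a model with a random intercept and slope per child.
- State which term decides: the active-arm slope for the endpoint as now written, and GROUP x linear run for any claim of superiority over sham.
- Keep the omnibus TIME and TIME x GROUP tests as descriptive. Show a quadratic term or the run means by arm as supportive, so that an early plateau is visible.
- Reconcile the number of runs across the synopsis and sections 6, 7.1.1, 8.1 and 11 before fixing the contrast.

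The cost is drafting, with no new data or visits. It is more than a change of analysis wording, since it amends the definition of a primary endpoint. It should therefore be made before the activation data are examined. The statistical cost is the lower sensitivity to an early plateau shown above.
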